Summary of changes for Protocol version 2.2 dated 13OCT2020.

Section(s)	Changes	Rationale
Study Team	Adding [name] to the study team as key personnel. Removing [name] and [name] from the Personnel section	Personnel changes

Summary of changes: Version 2.1 Dated 23MAR2020

Sections 6.1.6, section 8.1 and section 9 have been modified to include the following statement:

“Quality of life surveys will be sent to the patients’ personal email address. Completed responses will be sent directly to our REDCAP database.”

Summary of Changes: Version 2.0 Dated 18NOV2019

1. Page 8 Hypothesis: ARM 2 boost dose was incorrect and has been changed to 4200cGY.
2. Page 6 schema had N0-1 and this has been changed to N0. This has been made consistent across the protocol.
3. Section 7.3 Treatment duration section has been revised to state that, the whole breast will be treated for five consecutive fractions for either three (Arm 1) or two (Arm 2) consecutive weeks.

[figure not shown]
Informed Consent changes:

1. The footer of the informed consent has been changed to indicate the correct version of the protocol.

No other changes have been made in the informed consent.

SCHEMA

These exams, tests or procedures are part of regular cancer care and may be done even if you do not join the study.

Protocol Summary

Full Title: Prospective Randomized study of Accelerated Radiation Therapy (PRART): a Non-Inferiority Trial to Compare Breast Cosmesis and Local Control after Concomitant Boost Breast Radiotherapy with Fifteen Fractions in Three Weeks (arm 1, standard) versus Ten Fractions in Two Weeks (arm 2, experimental)

Short Title: Randomized

Clinical Phase: Phase III

Principal Investigators: Drs. [name] and [name]

Sample Size: N= 400 (200 per Arm)

Accrual Ceiling: 430

Rate of subject accrual: Approx. 8 subjects per month or 100 patients per year

Study Population: S/p segmental mastectomy patients with Tis (DCIS), T1-T2, N0 breast cancers.

Accrual Period: 4 years

Study Design: Patients with Tis (DCIS), T1-T2, N0 breast cancers will be randomized to receive whole breast radiotherapy with a concomitant boost to the tumor bed over 15 fractions (Arm 1, standard) versus 10 fractions (Arm 2, experimental).

Study Duration: 10 years to report: 2-3 years and 5 years late toxicity, local control rate, and breast cosmesis.

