8.1.1 Measuring the late toxicities of breast radiation

Radiation-induced breast fibrosis is another important late effect of radiotherapy with a commonly reported incidence of 5-15%. Clinically, radiation-induced breast fibrosis is characterized by skin retraction, atrophy, toughness to palpation, and decreased tissue compliance with associated functional limitations. Visual assessment and palpation are the most important clinical investigations of the skin in radiotherapy but they are subjective and unquantitative. The LENT/SOMA scoring system will be used in the reporting of late radiation morbidity in this protocol [24]. We will obtain measurement of breast fibrosis at baseline (prior to treatment) and at each subsequent follow-up after completing radiotherapy, scored by the research nurses assigned to the study.

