11 STATISTICAL AND DATA MANAGEMENT CONSIDERATIONS

Study Design: This study is a prospective randomized controlled trial to test the hypothesis that whole breast radiotherapy to 3200cGy with a concomitant tumor bed boost to 4200 cGy in 10 fractions (Arm 2,) is not inferior to standard whole breast radiotherapy with a concomitant tumor bed boost to 4800 cGy to the tumor bed in 15 fractions (Arm 1).

A total of 400 patients will be randomized to arm 1 or 2 to test the primary hypothesis that the proportion of patients with grade ≥ 2 acute toxicity with 2 weeks regimen would not be $> 5\%$ greater than the rate of 10% with a standard 3weeks regimen, with a 1-sided α of 0.025 and power of 79%.

The trial will have 2 planned interim analyses at 80 patients (20%; rejecting the null hypothesis when $Z \leq -4.88$, or $P \leq 0$) and at 240 patients (60%; rejecting the null hypothesis when $Z \leq -2.67$, or $P \leq 0.0038$) and a final analysis at 400 patients (100%; rejecting the null hypothesis if $Z \leq -1.98$, or $P \leq 0.0238$). The secondary objective was to test whether a significant difference exists between the 2 arms for long term fibrosis or telangiectasia grade ≥ 2 . The secondary objective has 1 planned interim analysis when 50% of the patients had completed 3 years of post-treatment follow-up (rejecting the null hypothesis if the hazard ratio was ≤ 0.37 , or $P < 0.0031$) and a final analysis when all the patients

had completed 3 years of follow-up (rejecting the null hypothesis if the hazard ratio was ≤ 0.63 , or $P < 0.049$).

The distributions of the baseline patient and disease characteristics at randomization for each arm will be summarized using descriptive statistics. Quantitative variables were summarized using the means, standard deviations, medians, and ranges; qualitative variables were summarized with frequency distributions of the nominal levels. Wilcoxon rank sum tests were used to compare the distributions of the quantitative variables between the 2 arms, and Fisher exact tests were used to compare the distributions of the qualitative variables between the 2 arms.

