To summarize the safety data, distributions of toxicity grades will be provided by treatment arm. Noninferiority tests will be conducted to test the primary hypothesis that the 2 weeks regimen would result in no more toxicity than did the 3 weeks regimen. Fisher exact tests will be used to compare the distributions of acute and late toxicity grades between the 2 weeks arm and the 3 weeks arm.

The comparison of the cumulative incidence of long term fibrosis or telangiectasia grade ≥ 2 between the 2 arms will be conducted using log-rank χ^2 tests. The hazard ratio between the 2 arms will be computed with the 95% confidence intervals.

Local recurrence-free survival will be estimated for both treatment arms using Kaplan-Meier curves, the relative risk will be estimated, and the 2 arms will be compared using the log-rank χ^2 tests.

11.1 Data management:

Data Management will be carried out by staff of the Department of Radiation Oncology at WCMC under the direction of [name]. Randomization will occur from a randomization list provided by [name]'s team and allocation to each arm will be performed, after consent is acquired, by the research team in the department of Radiation Oncology. The Randomization will be a manual process where the data manager will enter the consented patient's name in a sequential order in the Randomization list provided. Data will be entered into the JCTO Clinical database management system maintained by the JCTO according to the procedures of WCM. Patients will be followed every 12 months to evaluate their status with respect to recurrence. Recurrences will be evaluated using standard criteria in the Dept. of Radiation Oncology that are provided in the protocol. Data will be transferred from the Clinical database to the Division of Biostatistics for analysis. The Principal Investigator, Research Nurse and Data Manager have access to data collected.

Analysis: Patient characteristics at randomization will be summarized by treatment group using descriptive statistics and graphical displays.

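### The paired HR and P cut-offs for fibrosis or telangiectasia agree only near 35 interim and 73 final events, a count the plan neither states nor secures, and nothing says which cut-off governs

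*Combined protocol and SAP*

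**What the plan says.** Section 11 sets the question without direction: "The secondary objective was to test whether a significant difference exists between the 2 arms for long term fibrosis or telangiectasia grade" ≥2. It then gives two looks:

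- Interim: "The secondary objective has 1 planned interim analysis when 50% of the patients had completed 3 years of post-treatment follow-up". Rejection is at HR ≤0.37, or P<0.0031.
- Final: when all patients "had completed 3 years of follow-up (rejecting the null hypothesis if the hazard ratio was" ≤0.63, or P<0.049).

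The same section says that the comparison of cumulative incidence "between the 2 arms will be conducted using log-rank" χ² tests, and adds: "The hazard ratio between the 2 arms will be computed with the 95% confidence intervals". It does not say which arm is the numerator. It gives no event count, assumed event rate or power for this endpoint.

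The only incidence figure is in Section 8.1.1: "Radiation-induced breast fibrosis is another important late effect of radiotherapy with a commonly reported incidence of 5-15" per cent. It carries no grade and no time point, and it does not cover telangiectasia. The Protocol Summary gives a sample size of 400, 200 per arm.

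**The concern.** A hazard ratio cut-off and a P value cut-off are the same boundary at one event count only. With fewer events the same HR is weaker evidence. With more events it is stronger. The plan joins the two by 'or', fixes both in advance, and ties the looks to patient follow-up, so the event count will be whatever occurs. If the two halves then disagree, the text does not say which decides, and the choice could be made after the data are seen.

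The HR half also has a bound on one side only. The Protocol Summary and Sections 1.1 and 6.1.1 extend the non-inferiority aim to fibrosis, so excess fibrosis with the two-week schedule is the result that most needs a clear rule. At stake is a claim of a difference in late toxicity made at a looser error rate than planned.

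**Working it through.** **Inputs.** HR and P cut-offs: Section 11. Sample size 400, allocated 1:1: Protocol Summary. Incidence 5-15%: Section 8.1.1.

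**1. Reproduce the P values.** A two-look O'Brien-Fleming-type spending function (Lan-DeMets) at information fraction 0.5 and two-sided α 0.05 gives nominal P values of 0.0031 and 0.0490, as printed. The classical O'Brien-Fleming boundary gives 0.0052 and 0.0480, which do not match. The printed P values are therefore a two-sided 0.05 design.

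**2. Event count implied by each pair.** With 1:1 allocation, z = |ln HR|·√D/2, so D = 4(z/ln HR)².

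- Final: P = 0.049 two-sided gives z = 1.969, and ln 0.63 = −0.462. D = 4(1.969/0.462)² = 72.6. Rounding of the HR allows 70 to 75.
- Interim: P = 0.0031 gives z = 2.958, and ln 0.37 = −0.994. D = 4(2.958/0.994)² = 35.4. Rounding allows 34 to 36.

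The interim count is about half the final count, so the HR cut-offs look like translations of the P boundaries at about 73 events. That is 73/400 = 18%.

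**3. Events on the protocol's figure.** 5%, 10% and 15% of 400 are 20, 40 and 60 events.

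**4. What HR ≤0.63 means at other event counts.** Under no difference, the one-sided probability of an observed HR ≤0.63 is Φ(ln 0.63·√D/2). At 20 events this is Φ(−1.033) = 0.151. The HR that matches P = 0.049 is exp(−2 × 1.969/√D).

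| Final events | One-sided probability of HR ≤0.63 | HR equivalent to P = 0.049 (and its mirror above 1) |
|---|---|---|
| 20 | 0.151 | 0.41 (2.41) |
| 40 | 0.072 | 0.54 (1.86) |
| 60 | 0.037 | 0.60 (1.66) |
| 73 | 0.024 | 0.63 (1.59) |
| 80 | 0.019 | 0.64 (1.55) |
| 100 | 0.010 | 0.67 (1.48) |

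The intended value is 0.049/2 = 0.0245. Simulation with exponential event times and 3-year follow-up gives 0.159, 0.077 and 0.040 at 20, 40 and 60 events, in line with the formula.

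**5. Both looks, with the interim taken at half the events.** Using the HR cut-offs alone at both looks, the one-sided error is 0.169, 0.076 and 0.038 at 20, 40 and 60 final events, against 0.025. If either half of the 'or' suffices, the total two-sided error is 0.194, 0.101 and 0.063, against 0.05.

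**6. An example of disagreement.** Suppose the observed HR is 0.60 with 40 events. Then z = 0.511 × √40/2 = 1.615 and P = 0.106. The HR half rejects and the P half does not.

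**7. The other direction.** At 73 events an observed HR of 1.8 gives z = 0.588 × √73/2 = 2.51 and P = 0.012, so the P half rejects. For a true HR of 2.0, the chance that P<0.049 flags it at the final look is 34%, 59% and 76% with 20, 40 and 60 events.

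**8. Interim timing.** Half the patients at 3 years need not be half the information. Assuming uniform accrual over the planned 4 years, a constant hazard of 0.02-0.065 per year, and looks at years 5 and 7, the fraction is 0.61-0.63 if all follow-up counts, or 0.84 if follow-up is cut at 3 years. Keeping the printed P boundaries, the two-sided error is 0.0500, 0.0496 and 0.0490 at fractions 0.50, 0.61 and 0.84.

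**The case against.** The strongest reply is that 'or' here joins two expressions of one boundary. The primary-endpoint rule in the same section does this with Z and P, and the HR and P values do match each other at 35 and 73 events. On that reading P governs and there is no inflation. This is plausible and limits the finding. It does not remove it, because a Z value and a P value correspond at any sample size, whereas an HR and a P value do not. The text leaves open what to do when they part.

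Second, 20-60 is not the endpoint's own event count. The 5-15% is for fibrosis of unstated grade and time point, and the endpoint adds telangiectasia and requires grade ≥2. The true rate could be lower or higher. If 5-15% were a 3-year rate and later follow-up counted (uniform 4-year accrual, final look at year 7), the range would be about 33-94 events, which includes 73. This stands: a shortfall is likely on the protocol's figure but not proven.

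Third, a reader might infer from the ≤ signs that the rule rejects only when Arm 2 is better and cannot flag harm. The documents do not support that. The P half belongs to a two-sided boundary, the log-rank χ² has no direction, and the numerator arm is never named, so even the reading that a low HR favours Arm 2 is an assumption. Section 11 also plans Fisher exact tests on late toxicity grades, which have no stated direction either.

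A reader might likewise infer that the interim timing inflates the error. Step 8 shows that it is slightly conservative.

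**Conclusion.** The concern holds in limited form. The HR and P cut-offs agree only near 35 interim and 73 final events, no event count is planned, and the plan does not say which half decides.

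The size depends on the event count and on the HR being used to decide. The 0.15 figure belongs to the 5% floor; at 15% incidence the excess is modest (0.037 against 0.0245). There is none if P governs. Above 73 events the HR cut-off errs towards strictness.

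The rule as a whole is not blind to excess fibrosis. Only its HR half is one-directional, although the chance of detecting excess fibrosis through P is limited when events are few.

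The results rest on the usual large-sample log-rank approximation with 1:1 allocation and, for the two-look figures, on an interim at half the events. The acute-toxicity primary analysis is unaffected. Severity: should-fix.

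**What to change.** In Section 11:

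1. Remove HR ≤0.37 and HR ≤0.63 as decision criteria. If they are kept for information, label them as illustrative at about 35 and 73 events.
2. State that the two-sided log-rank P boundaries alone govern, in both directions, so that excess and reduced fibrosis are judged by the same rule.
3. Recalculate the O'Brien-Fleming-type spending at the observed event fraction at the interim. State the total event count used as the denominator, and whether events after 3 years are included.
4. Define the HR as Arm 2 over Arm 1. Keep the planned 95% confidence interval and add the difference in 3-year cumulative incidence with its 95% interval.

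This costs a wording amendment, with no extra patients or data. It should be settled before anyone sees the fibrosis comparison by arm, so that the criterion cannot be chosen afterwards.

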1 OBJECTIVES

1. To prospectively randomize patients to one of two fractionation regimens of whole breast radiotherapy with a concomitant boost as part of breast conservation therapy in post-menopausal women with T1-2 N0 breast cancers or Stage 0 (Tis) DCIS: 4050 cGy whole breast radiotherapy with a concomitant tumor bed boost to 4800 cGy to the tumor bed in 15 fractions (Arm 1) versus 3200cGy whole breast radiotherapy with a concomitant tumor bed boost to 4200 cGy in 10 fractions (Arm 2).
2. To assess the rate of acute toxicity (grade 3 or higher).
3. To assess the rate of long-term fibrosis (grade 3 or higher) and changes in breast cosmesis in the 2 arms at 2-3 years and at 5 years.
4. To assess and compare local control at 2-3 years and at 5 years between the two arms.

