1.1 Study Hypothesis

A hypo-fractionation breast radiotherapy regimen delivered over two weeks is not inferior to standard treatment over three weeks (whole breast radiotherapy with a concomitant boost), in terms of acute toxicity and long term fibrosis, breast cosmesis and local control, at 2-3 years and at 5 years follow up.

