where α / β is a tissue dependent parameter, arising from the radiobiological linear - quadratic cell survival model.

From the randomized prospective trials, there is an estimate that breast cancer may have an alpha/beta for tumor control of 4.6 and normal breast tissue an alpha beta ratio of 3.4 [6]. The relative closeness in alpha/beta ratios of tumor and normal tissue would support a rationale for hypo-fractionation [20-23]. Based on the formula above, Table 1 includes the calculation of BEDs (biologically equivalent doses) between the 2 arms. The breast cavity is predicted to have an alfa/beta value between 3-4.

Based on Table 1 a regimen of 42 Gy in 10 fraction to the boost is comparable to 48 Gy in 15 fractions. The latter regimen has been proven to both be effective (local recurrence rate <5% at 5 years) and to be associated with excellent cosmetic results (16), justifying our choice for a biologically equivalent regimen) in the experimental arm comparable to standard arm (see α/β values in Table 1, in bold).

In view of the fact that most recurrences tend to occur at the original tumor bed and that other studies have shown efficacy of lower doses of adjuvant radiation to the rest of the breast (4-8), we elect to test a dose of 32 Gy in 10 fractions. Maintaining a relative low dose to the rest of the breast tissue, which is a much lower risk of local recurrence than the area of the tumor cavity, will reflect on very low risk of fibrosis and will enhance the likelihood of optimal breast symmetry and cosmesis.

TABLE 1

Alfa/Beta (Gy)	2 Gy x 23	2.7 Gy x 15	3.2 Gy x 15*	3.2 Gy x 10	4.2 Gy x 10*
2	46	47	62.4	41.6	65.1
3	46	46.1	59.5	39.68	60.48
4	46	45.2	57.6	38.4	57.34
10	46	42.8	52.8	35.2	49.7

- Boost Dose delivered at tumor bed

3 Staging Criteria

TNM Stage 0 (Tis N0 M0), Stage I-II, T1-2 N0 M0, newly diagnosed breast cancer patients.

4 Patient Eligibility

Inclusion criteria:

1. Women status post segmental mastectomy
2. If unilateral, pT1-2 breast cancer excised with negative margins
3. If bilateral, pT1-2 breast cancer excised with negative margins AND/OR pTis excised with negative margins.
4. Clinically N0 or pN0 or sentinel node negative
5. Ductal carcinoma in situ DCIS with negative margins (no DCIS on inked margins).
6. Women with previous contralateral breast cancer.

Exclusion criteria:

1. Previous radiation therapy to the ipsilateral breast.
2. 90 days from last surgery, unless s/p adjuvant chemotherapy

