3. 60 days from last chemotherapy
4. Male breast cancer

5 Descriptive Factors/Stratification/Randomization Scheme

This is a prospective, randomized study. No stratification is planned. The study schema describes the study design.

5.1 Study Schema /Table 2

Eligibility	Stage 0 or Stage I-II breast cancer s/p segmental mastectomy.	
Day 0	Informed consent and randomization CT planning for determination of tumor bed on the prone position	
Days 1-15 (start within 90 days from last breast surgery)	Weekly IGRT, IMRT or Conformal breast irradiation, randomly assigned to: 15 fractions whole breast radiotherapy with concomitant boost (arm 1) or 10 fractions whole breast radiotherapy with concomitant boost (arm 2)	
Note: Patients with bilateral breast cancer will be randomized to receive the same dose and fractionation to both breasts		

6 Treatment plan

6.1.1 The women in this study will be randomly assigned to receive either 10 or 15 radiation fractions. The study design permits to test non inferiority of the 2 weeks versus 3 weeks regimen in terms of acute toxicity, fibrosis, breast cosmetic results and local control at 2-3 years and at 5 years follow up.

6.1.2 The informed consent process is as follows. The principal investigator explains all elements of the protocol to the patients and answers any and all questions. Clinical procedures are performed by the principal investigator. The research nurse will obtain blood sample by venipuncture. The consent process takes place in the Department of Radiation Oncology at Weill Cornell Medical Center. The consent form process is concluded when the patient, principal investigator and the witness all have signed the consent form. The witness is a present adult able to verify that the patient was given the proper information needed to make an informed decision to participate in the clinical study. year 1

6.1.3 Once the process of randomization is concluded, patients will be informed of the schedule based on the assigned one of the 2 arms.

6.1.4 Simulation and treatment will be started within 90 days from surgery, in order to maximize the chances of optimal lumpectomy cavity visualization on the planning and cone beam CT scans.

6.1.5 Our routine follow up is once a year after completion of radiation therapy. For the purpose of protocol significance (for assessment of fibrosis), we will require at least one follow up visit to our department, after years 2. (See 11.1 Study calendar).

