17 COST TO SUBJECTS

Each subject or their insurance company will be charged and held responsible for the costs of care provided as part of this study. Radiotherapy is a standard treatment for breast cancer and will be billed to subjects and their insurance companies.

There will be no monetary compensation for participating in this study.

18 APPENDIX 1 - LENT/SOMA Criteria: Late Reactions

Table 1. RTOG/EORTC and LENT/SOMA classification of late effects				
RTOG/EORTC	Grade 1	Grade 2	Grade 3	Grade 4
Skin	Slight atrophy, pigmentation change, some hair loss	Patchy atrophy, moderate telangiectasia, total hair loss	Marked atrophy, gross telangiectasia	Ulceration
Subcutaneous tissue	Slight induration (fibrosis), and loss of subcutaneous fat	Moderate fibrosis, but asymptomatic; slight field contracture, $\leq 10\%$ linear reduction	Severe induration and loss of subcutaneous tissue, field contracture, $\geq 10\%$ linear reduction	Necrosis
LENT/SOMA				
Breast				
Subjective				
Pain	Occasional and minimal	Intermittent and tolerable	Persistent and intense	Refractory and excruciating
Objective				
Telangiectasia	$< 1 \text{ cm}^2$	$1-4 \text{ cm}^2$	$> 4 \text{ cm}^2$	
Fibrosis	Barely palpable, increased density	Definite increased intensity and firmness	Very marked density, retraction, and fixation	
Edema	Asymptomatic	Symptomatic	Secondary dysfunction	
Retraction, atrophy	$10-25\%$	$> 25-40\%$	$> 40-75\%$	
Ulcer	Epidermal only, $< 1 \text{ cm}^2$	Dermal only, $> 1 \text{ cm}^2$	Subcutaneous	Whole breast Bone exposed, necrosis
Lymphedema, arm circumference	$2-4\text{-cm}$ increase	$> 4-6\text{-cm}$ increase	$> 6\text{-cm}$ increase	Useless arm
Skin				
Pigmentation change	Transitory, slight	Permanent, marked	—	—
Abbreviations: RTOG = Radiation Therapy Oncology Group; EORTC = European Organization for Research and Treatment of Cancer; LENT = Late Effects Normal Tissue Task Force; SOMA = subjective, objective, management, and analytic.				

Please, refer to the following link for the Common Terminology Criteria for Adverse Events, version 5.0

https://ctep.cancer.gov/protocoldevelopment/electronic_applications/docs/ctcae_v5_quick_reference_5x7.pdf

19 Appendix 2 - Toxicity Tracking Form

PHYSICIAN'S PROGRESS NOTE

Fraction: ☐ 1-5 ☐ 6-10 ☐ 11-15 ☐ 1 mo F/U ☐ 3 mo F/U

The following critical elements of the patient's weekly exam have been covered:

- ☐ *Chart & Dosimetry, Treatment set up & positioning review*
☐ *Port Film or image review*

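### The late fibrosis event in Section 11 makes no use of the pre-radiotherapy score, so firmness already present before treatment can dilute the hazard ratio

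*Combined protocol and SAP*

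**What the plan says.** Section 11 plans "The comparison of the cumulative incidence of long term fibrosis or telangiectasia grade" ≥2 between arms by log-rank tests, with a hazard ratio and 95% confidence interval. It describes the aim as to "test whether a significant difference exists between the 2 arms for long term fibrosis" or telangiectasia, and it gives no margin for this endpoint. Section 1.1 nevertheless states the hypothesis for fibrosis, among other outcomes, as the two-week regimen "is not inferior to standard treatment over three weeks".

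Section 8.1.1 provides the baseline: "We will obtain measurement of breast fibrosis at baseline (prior to treatment) and at each subsequent follow-up after completing radiotherapy". The Protocol Summary (Endpoints) says the same of LENT/SOMA scoring generally. Neither Section 10 nor Section 11 refers to that baseline score again.

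On timing relative to surgery, Section 6.1.4 says "Simulation and treatment will be started within 90 days from surgery". The Section 4 exclusion carries an exception: "90 days from last surgery, unless s/p adjuvant chemotherapy". Appendix 1 describes LENT/SOMA grade 2 fibrosis as "Definite increased intensity and firmness".

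Section 9 and the Protocol Summary place the fibrosis assessment at 2-3 years and at 5 years. Section 1, objective 3, sets the fibrosis threshold at grade 3 or higher, whereas Section 11 uses grade 2 or higher.

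**The concern.** The grade 2 descriptor records what the examiner feels, not what caused it. A breast operated on within the previous three months may already feel firm when the pre-radiotherapy score is taken. If that firmness is still there at a late visit, Section 11 gives no rule for keeping it out of the event count. Two analysts could treat the same patient differently, and both could claim to follow the plan.

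Randomization makes such carried-over events equally likely in the two arms, so they add the same share to both and move the hazard ratio toward 1. The late comparison is a test of difference attached to a hypothesis of non-inferiority with no fibrosis margin. A diluted hazard ratio and a non-significant test could then be taken as reassurance that the regimen has not earned.

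**Working it through.** **1. The plan's own figures.** Section 11 gives rejection boundaries for the late endpoint of hazard ratio ≤0.37 (P<0.0031) at 50% and ≤0.63 (P<0.049) at the end. A two-look O'Brien-Fleming-type spending boundary at 50% and 100% information, two-sided 0.05, gives P = 0.00305 and 0.0490, so the P values reproduce. Implied events with 1:1 allocation are 4z²/(ln HR)²:

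- interim: 4 × 2.958² / (ln 0.37)² = 35.4
- final: 4 × 1.969² / (ln 0.63)² = 72.6

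The ratio is 0.49, which agrees with a half-way look. The plan states no event count. About 73 events is 73/400 = 18%. The fibrosis incidence of 5-15% in Section 8.1.1 would give 20 to 60, although the composite also counts telangiectasia.

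**2. Dilution.** Inputs: 200 per arm (Protocol Summary); Arm 1 radiation fibrosis p₁ = 10%, the middle of 5-15% (Section 8.1.1). Assumptions not in the documents: a true hazard ratio of 2.0, so p₂ = 1 − 0.90² = 19%; and a share b of each arm that is at grade ≥2 before radiotherapy and stays there.

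Observed risk q = b + (1 − b)p. Observed hazard ratio = ln(1 − q₂)/ln(1 − q₁). The risk difference becomes (1 − b)(p₂ − p₁). For b = 10%: q₁ = 0.10 + 0.90 × 0.10 = 0.190; q₂ = 0.10 + 0.90 × 0.19 = 0.271; hazard ratio = ln 0.729/ln 0.810 = 1.50; difference 8.1 points instead of 9.0.

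**3. Power at two-sided 0.049.** A two-proportion calculation was checked with 3,000 simulated log-rank trials per setting (Monte Carlo standard error at most √(0.25/3000) = 0.9 points). Carried-over events sit at the 1-month visit in the simulation; the two-proportion version does not depend on when they occur. "New only" drops patients at grade ≥2 before radiotherapy.

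| b | Arm 1 v Arm 2 observed | Difference (points) | Hazard ratio | Two-proportion power: all / new only | Log-rank power: all / new only |
|---|---|---|---|---|---|
| 0% | 10.0% v 19.0% | 9.0 | 2.00 | 72.3% / 72.3% | 72.8% / 72.8% |
| 5% | 14.5% v 23.05% | 8.55 | 1.67 | 58.8% / 70.1% | 56.8% / 70.1% |
| 10% | 19.0% v 27.1% | 8.1 | 1.50 | 48.2% / 67.7% | 44.2% / 69.5% |
| 20% | 28.0% v 35.2% | 7.2 | 1.32 | 33.7% / 62.6% | 29.1% / 63.5% |

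**4. Other settings, for b = 0, 5, 10, 20%.**

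- Arm 1 at 15%, hazard ratio 2.0: observed 2.00, 1.76, 1.61, 1.42; log-rank power 87.0, 77.6, 67.2, 48.2% (new only 87.0, 86.2, 84.2, 79.6%).
- Arm 1 at 5%, hazard ratio 2.0: observed 2.00, 1.50, 1.33, 1.19; two-proportion power 44.0, 28.0, 20.6, 13.5% (new only 44.0, 42.2, 40.3, 36.5%).
- Arm 1 at 10%, hazard ratio 1/0.63 = 1.59: observed 1.59, 1.40, 1.29, 1.19; log-rank power 36.3, 26.1, 21.5, 15.1% (new only 36.3, 35.0, 35.6, 31.4%).

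**5. No true difference.** With 10% in both arms and b = 10%, the simulated rejection rate toward more fibrosis in Arm 2 is 2.3%, against a nominal 0.049/2 = 2.45%.

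**6. Partial persistence.** The effective b is prevalence times persistence. A 10% baseline prevalence of which half persists behaves as b = 5%.

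**The case against.** A reader might infer that the plan counts every grade ≥2 score, including firmness at the 1-month visit. The documents do not support that. Section 11 is silent on baseline status rather than inclusive. Cumulative incidence ordinarily means new onset, and Section 8.1.1 calls the condition radiation-induced. Section 9 and the Protocol Summary place fibrosis at 2-3 and 5 years, so collecting a 1-month score does not make it a late event. Section 13.1.1 also records pre-existing conditions, though for adverse event reporting rather than LENT/SOMA scoring.

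A reader might also infer that surgical firmness does carry over and hides harm in Arm 2. Nothing in the documents shows how many patients are at grade ≥2 before radiotherapy or how many remain so. Only firmness lasting to the late assessment matters, and after chemotherapy the interval from surgery can exceed 90 days. Telangiectasia is not a firmness measure. Nor do the documents predict more fibrosis in Arm 2: in Table 1, at α/β of 3, the whole-breast figure is lower (39.68 v 46.1) and the boost figure slightly higher (60.48 v 59.5). The hazard ratio of 2.0 is an illustration, and its 19% in Arm 2 lies above the quoted 5-15%.

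Nor is the dilution an automatic gain for Arm 2. If the Section 11 boundaries refer to Arm 2 over Arm 1, dilution makes them harder to reach. It helps Arm 2 only where non-significance is read as non-inferiority, which is a separate weakness.

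All of this limits the size and certainty of the problem. It does not supply the missing rule. The new-onset reading is available but nowhere stated, and the baseline score that would settle it goes unused.

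**Conclusion.** The point holds as a gap in the definition of a secondary endpoint. The late event has no stated relation to the pre-radiotherapy score, and the comparison is not adjusted for it. Firmness that predates radiotherapy and persists can be counted in both arms, which dilutes the hazard ratio and lowers power to see more fibrosis in Arm 2. It does not raise the false-positive rate, and the absolute difference shrinks only by the factor 1 − b.

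The size cannot be fixed from the documents. Over an assumed 5% to 20% carry-over, equal in both arms and fully persistent, a true hazard ratio of 2.0 appears as about 1.7 to 1.3 with Arm 1 at 10%. If carry-over is near zero or resolves before year 2, the effect is small. It would probably also be smaller at the grade 3 threshold of Section 1, whose Appendix 1 description is much more severe. The two thresholds therefore need to be reconciled before the event can be defined.

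**What to change.** In Section 11:

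- Define the late event as fibrosis or telangiectasia of grade ≥2 that is at least one grade above the patient's own pre-radiotherapy LENT/SOMA score for that item.
- Tie the event to the protocol's existing late assessments at 2-3 years and 5 years, rather than introducing a new cut-off.
- Stratify or adjust the comparison for pre-radiotherapy grade, and report those grades by arm.
- Keep the count of any grade ≥2, regardless of baseline, as a sensitivity analysis.
- Reconcile the grade ≥2 threshold in Section 11 with grade ≥3 in Section 1, objective 3.

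The baseline score and late visits are already in the protocol, so for most patients this is a change of wording. If the event is to be defined per breast in bilateral cases, the protocol must also say that each breast is scored, which it does not now do.

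The cost is fewer counted events. The new-only calculation above approximates this rule: it drops patients at grade ≥2 before radiotherapy, whereas the proposed definition keeps them and counts them if they worsen. In the 10% v 19% setting with 10% carry-over, simulated power is 69.5% with new events only, against 44.2% when all are counted.
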